## Study Protocol:

### 1. Objectives:

**Primary GOAL:** Compare efficacy and safety of prophylactic indomethacin, DCC, and their combination, in affecting the incidence and severity of IVH in infants less than 29wks GA at birth.

- **Aim 1A):** Test for differences in primary outcome measure: 'fraction of survivors with no severe IVH or PVL' among the 4 groups, using head ultrasound (1-30d), and head MRI at 38wks adjusted GA.
- **Aim 1B):** Test the hypothesis that DCC improves effectiveness and/or decreases toxicities of indomethacin.
- **Aim 1C):** Test for treatment dependent differences in neurocognitive follow up evaluations and investigate relationships between short term brain imaging results and later neurocognitive performance across treatment groups.

**Secondary GOAL:** Investigate mechanistic effects of prophylactic indomethacin, DCC, and their combination in infants less than 29wks GA.

- **Aim 2A):** Test the hypotheses that blood volume status and/or hemodynamic stability are different between groups (at 0,1,2,3,7, 30, and 60 days of life).
- **Aim 2B):** Test the hypothesis that biomarkers of inflammation and vascular endothelial stress are different between groups (at 0,1,2,3,7, 30, and 60 days of life).
- **Aim 2C):** Test the hypothesis that numbers, or apoptotic frequency, of circulating progenitor cells with endothelial or neuronal phenotype capacity are different between groups (at 0,1,2,3,7, 30 and 60 days of life).
- **Aim 3):** Determine relationships between clinical outcomes (Aim1) and blood measurements (Aim 2) among treatment groups.

### 2. Study Design:

***The study design of this research project is a randomized, blinded investigation of 4 treatment groups:***

- 1) Control (no intervention);
- 2) DCC alone;
- 3) Prophylactic indomethacin alone;
- 4) Combination of DCC/indomethacin

Infants randomized to block randomization with blocks of size 8 each to randomly assign the subjects into one of the 4 groups. The randomization table will be prepared in advance by the statistician and clinicians will be blinded to this choice prior to the delivery. Investigational Drug Services will provide indomethacin dosing solutions and placebo dosing solutions that are matched in appearance and volume for each study participant. Please note that randomization will occur in all cases, but the attending Neonatologist at delivery and bedside will have authority to define care; if this physician has an objection to the randomization of indomethacin treatment for a specific patient that patient will be excluded from the study. Similar provisions are afforded to the delivering Obstetrician regarding delay of umbilical cord clamp randomization and treatment.

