### 3. Study Population:

It is anticipated that this study will begin July, 2014 and will enroll subjects through June 31 of 2019. Follow-up in NICU Graduate Clinic will continue thru June 31, 2020. We are going to enroll 400 infants during that time, male and female all inborn at the University of Kentucky. The population is primarily Caucasian (80%), African American (15%), Asian (3%), and a Hispanic population of about 2%. All races and ethnicities will be included if subjects parent(s) are able to understand English (spoken or written). Pregnant women are considered to also be research subjects in this trial. When the pregnant mother is a

legal adult (18yrs or older) their consent will include their participation as well as their infant. Pregnant women whom are less than 18yrs and greater than 14yrs of age and qualify for enrollment criteria will also be invited to participate in this study. In these cases assent will be obtained from the pregnant mother (who is considered a legal minor), and consent will be obtained from the pregnant mother's legal guardian.

Inclusion criteria

- Neonates with a GA less than 29 6/7weeks (based on last menstrual period and/or early pregnancy ultrasound)
- Consent obtained prior to delivery

Exclusion criteria

- neonates with congenital anomalies such as congenital heart disease
- a prenatal plan to withhold neonatal care
- maternal risks identified by obstetrician, including severe hemorrhage (placenta abruption or placental previa), hypertensive crisis
- if the attending obstetrician or neonatologist decides that infant requires immediate resuscitation for either maternal or newborn well-being
- any prenatal indocin use within 72 hours before birth

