**4. Subject Recruitment Methods and Privacy: Recruitment:**

[figure not shown]
A total of 400 premature infants born <29 6/7weeks GA will be recruited from the obstetrics admission area and randomized to one of the 4 treatment groups; n=100 each will complete the study (control; DCC alone; Indomethacin alone; DCC + Indomethacin). This facility admits over 800 sick newborn infants/yr and sees a majority of the high-risk obstetrical patients in the Lexington area and beyond. Informed consent will be obtained prior to patient enrollment, by [name] (PI) or another member of the research team experienced at consenting mothers for research studies. There will also be an on-call schedule at night to screen potentially eligible women, enroll them, and attend the births. Women enrolled will be assigned to either immediate or delayed cord clamping groups via a computer generated random number system to assure permuted block randomization. When notified of a subject's impending birth, the research coordinator will open the randomization card, review the protocol with the attending/fellow/or resident obstetrician, and time the cord clamping.

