If for any medical reason the bedside/attending Obstetrician or Neonatologist has concerns and wishes to become ‘unblinded’ to the infant’s enrollment, the study participant will be removed from the study. We expect that the only practitioner who is unblinded in the study is the specific Neonatologist at the particular infants’ delivery, who most likely is not performing the daily care for the newborn after admission based on the structure of our delivery room teams and NICU service teams. All study infants will routinely be followed-up at UK NICU Graduate Follow-up Clinic after discharge since these clinicians have the primary responsibilities for this standard clinical service in our institution. Research oversight for neurodevelopmental follow-up will be the responsibility of [name]. The TIMP and Bayley Scales of Infant Development-III (BSID-III) will be administered at 3-4, 6-9, and 18-24 months corrected age; these are the standard follow-up times for collection of such data in our clinic, and the tests proposed has been optimized and defined for these age intervals. All exams will be performed by the same therapist trained in high-risk newborn neurodevelopmental exams to avoid performance biases, and will be blinded to the treatment group. Data will be reviewed quarterly by the research team. Money will be given to families (\$25) for expenses (gas, parking, food) for each of the three follow-up evaluations. Frequent phone contact with project personnel has been another technique successfully used in past research by [name] and colleagues. Project personnel will contact participants every 2 weeks until the first measurement (3-4 months), and then monthly until all measurements are complete for the follow up groups (n=400 completed). Participants will be asked to give multiple phone numbers (work, family, and friends) to make contact more feasible; participants who move or change phone numbers will receive gift certificates (\$25) if they contact research personnel with their new address or phone number. Some attrition (~5%) is anticipated and is built into the sample size calculation.

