**Aim 1 Statistical analyses: [all analyses performed as 'intention to treat' where appropriate]:** To investigate the primary hypothesis in Aim 1A (treatment-related outcome differences with respect to the primary endpoint fraction of cases surviving without severe IVH, grade 3 or 4) we will use head ultrasound data from day of life 0-30, and use two distinct approaches. First, based on the qualitative data used to compute the sample size, we will employ a bivariate analysis to identify the significant covariates, followed by a multiple logistic regression analysis to test for differences between the four groups in the presence of significant covariates. Secondly, we will develop severe IVH or PVL data and employ survival analysis statistics (log rank Mantel-Cox test). If the assumptions are validated, we will use the Cox proportional hazard model for this survival data. In addition we will compare head MRI results (measured at the single time point of 38wks adjusted gestational age using a multiple regression model that will incorporate significant covariates. Aim 1B is concerned with comparison of Groups 3 and 4 only (e.g. Indomethacin vs. Indo-DCC) and the procedures developed for the 4 group analysis are also applicable here. For Aim 1C we correlate later performance with the short term brain imaging results in the framework of a multiple regression model where the 4 groups will be used as predictors and will be compared. In all settings we will also perform separate analyses of IVH alone, and PVL alone.

Aim 1 also involves comparisons of nominal/ordinal and continuous variables associated with neurodevelopment and toxicity where single or repeated measures on the response are available. Approaches similar to the one described above will be taken where we first build a statistically valid model that controls for all influential covariates and test the relevant hypotheses in the context of the model. Aim 1B corresponds to the testing of the interaction effect between the ICC/DCC effect and the use of prophylactic indomethacin. Other hypotheses correspond to the main effects. We will also compare the variables that reflect renal function/status (as assessments of potential indomethacin toxicities, other specific comorbidities and hospital stay related variables across the 4 groups.

**Aim 2: Investigate mechanistic effects of prophylactic indomethacin, DCC, and their combination in infants less than 28wks gestational age.**

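### The log-rank test, one of two unranked approaches to the primary hypothesis, uses no strata or covariates, so it leaves chance imbalance in gestational age uncorrected and may lose some power

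*Combined protocol and SAP*

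**What the plan says.** **Allocation.** Section 2 (Study Design) states "Infants randomized to block randomization with blocks of size 8 each to randomly assign the subjects into one of the 4 groups". Section 4 (Subject Recruitment Methods and Privacy) says women are assigned to a cord-clamping group "via a computer generated random number system to assure permuted block randomization". Neither section names a stratification factor.

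**Size.** Section 3 plans 400 infants, and Section 4 says "n=100 each will complete the study".

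**Gestational age.** It defines eligibility in Section 3: "Neonates with a GA less than 29 6/7weeks (based on last menstrual period and/or early pregnancy ultrasound"). No lower limit is given. It is therefore known before birth, and Section 4 has the card opened when birth is impending.

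**Analysis.** For the primary hypothesis, the Aim 1 statistical analyses say "we will use head ultrasound data from day of life 0-30, and use two distinct approaches". The first approach is logistic regression on the four groups, with covariates that pass a bivariate screen. The second will "employ survival analysis statistics (log rank Mantel-Cox test"). A Cox model follows if its assumptions hold, but its covariates are not listed. The two approaches are not ranked, and gestational age is not named as a covariate in either.

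**Power.** The Aim 3 statistical analyses say that the study was powered on chi-square tests of proportions and that controlling for influential covariates should generally improve on that power.

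**The concern.** Blocks of 8 keep the four arms close in size but do nothing to balance gestational age across them. A plain log-rank test compares the arms as they fall. If one arm happens to receive more of the least mature infants, and immaturity raises the risk of the outcome, that arm looks worse and nothing in the test corrects it.

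Ignoring a prognostic factor also costs power. The plan expects covariate control to improve power, but the log-rank test controls for nothing. The Cox model may never be used, and if it is, the plan does not say that it will carry gestational age. With 100 infants per arm and a comparison across four groups, a few points of power are worth keeping when the variable is already collected for eligibility.

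**Working it through.** **Inputs from the documents.** Four arms of 100, blocks of 8, no stratum named, and ultrasound on about days 3, 7, 14 and 30. The documents give no event rates, no risk by gestational age and no distribution of gestational age. The stated sample size cannot be reproduced for the same reason.

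**Assumed inputs.** The share *s* of infants in a younger band is 30%, 40% or 50%. Outcome risk (younger v older band) is 30% v 15%, 35% v 10% or 45% v 10%.

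**Step 1: how often imbalance occurs.** With 100 per arm, the number in the younger band is taken as binomial in each arm. The SE of the difference in share between two arms is √(2·s(1−s)/100), and the table gives the chance of each gap.

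| s | SE (points) | Given pair, gap ≥10 | Given pair, gap ≥15 | Highest v lowest of four, gap ≥10 | Highest v lowest of four, gap ≥15 |
|---|---|---|---|---|---|
| 30% | 6.5 | 14% | 2.5% | 46% | 11% |
| 40% | 6.9 | 17% | 3.6% | 52% | 15% |
| 50% | 7.1 | 18% | 4.0% | 54% | 17% |

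**Step 2: what a 10-point gap does to a comparison of two arms.** Shift = gap × difference in risk between the bands.
- 30% v 15%: 0.10 × 15 = 1.5 points
- 35% v 10%: 0.10 × 25 = 2.5 points
- 45% v 10%: 0.10 × 35 = 3.5 points

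For scale, at an assumed 20% event rate the SE of a difference between two arms is √(2 × 0.20 × 0.80/100) = 5.7 points. A 2.5-point shift is a little under half of one SE.

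**Step 3: type I error.** Trials of 4 × 100 in blocks of 8 were simulated with no treatment effect, using 3-df tests at 0.05. Gestational age was continuous, with hazard ratios (HR) of 1.0 to 2.5 per SD, and control event rates were 20% or 35%. The plain log-rank test rejected in 3.9-5.5% of trials overall. In the fifth of trials with the largest imbalance it rejected in 5-8% at HR 1.5-2.0 and in 7-9% at HR 2.5 (about 300 runs each, SE about 1.3-1.7 points). In the two-band model, among trials with a gap of 15 points or more, the plain test rejected in about 7% and the stratified test in 4-6%.

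**Step 4: power, plain against stratified log-rank, with unstratified allocation.** Several simulations were run in the two-band model, with lesions dated to the ultrasound days. Absolute power depends on the assumed treatment effect and lesion timing, so the difference is the useful figure.
- 30% v 15%: gain of about 0-2 points (for example 63% to 64%)
- 35% v 10%: gain of about 3 points (60% to 63%; 59% to 62%)
- 45% v 10%: gain of about 5-7 points (67% to 73%; 62% to 69%)

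The continuous model agrees in direction. At a 35% control rate, stratifying by thirds of gestational age moved power from 81.7% to 82.5% (HR 1.5 per SD), 80.1% to 84.4% (HR 2.0) and 76.2% to 83.1% (HR 2.5). At a 20% control rate the gains were 1.0, 1.8 and 3.8 points. With HR 1.0 there was no material difference.

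**Step 5: what stratified allocation adds.** With both allocation and test stratified, power was 63% at 35% v 10% and 75% at 45% v 10%, against 63% and 73% for the stratified test alone. The Monte Carlo SE of the 2-point difference is √(0.73 × 0.27/2000 + 0.75 × 0.25/2000) = 1.4 points, so no clear gain is shown. A plain log-rank test after stratified allocation was conservative, rejecting in about 2-4% under the null at the two steeper gradients.

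**The case against.** The strongest reply is that nothing here is invalid. Chance imbalance is part of the sampling variation that an unadjusted test already allows for, and Step 3 bears this out. That stands. A reader might infer that the missing strata bias the primary result or inflate its false-positive rate, but the planned design does not support that. The harm is conditional on the imbalance that occurs, plus some lost efficiency.

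Second, the documents never call gestational age the main prognostic factor. The high-risk wording in Section 6 describes the whole enrolled group, not a gradient within it. That also stands. Using gestational age here is a judgement, supported by its role in eligibility, and the size of the effect is assumed.

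Third, about half of trials show a 10-point gap only between the most extreme of four arms. For a given pair the figure is 14-18%, and the shift in Step 2 belongs with the pairwise figure.

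Fourth, the plan adjusts elsewhere. The logistic approach uses covariates, and a Cox model may follow. This helps only in part. Gestational age enters the logistic model only if it passes the screen, and the Cox model is conditional with no covariates listed.

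Finally, Section 4 contains a figure that is not reproduced, and the randomisation table is not part of the documents. A stratum could be named there, so the sponsor should confirm. That would not change the point about the log-rank test.

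**Conclusion.** The point holds as a modest matter of efficiency and of protection against an unlucky allocation. As written, the second approach to the primary hypothesis takes no account of gestational age, and the text names no stratum in the allocation.

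The cost depends on how strongly gestational age predicts the outcome: almost nothing for a weak gradient, about 3 points of power at 35% v 10%, and 5-7 points at 45% v 10%. When a given pair of arms does differ by 10 points in the younger-band share, that comparison moves by about 1.5-3.5 points. All of these figures rest on assumed risks and band shares.

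A reader might also infer that unstratified allocation is itself the main fault. The figures do not support that, because nearly all the gain comes from the analysis.

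**What to change.** In the Aim 1 statistical analyses:
1. Replace the log-rank test with one stratified by a gestational-age band whose cut point is fixed before outcome data are seen.
2. Stratify the Cox model by the same band, or adjust it for gestational age.
3. Include gestational age in the four-group logistic model whatever its p-value in the bivariate screen.

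This is a short edit to the analysis plan. It needs no new data and remains possible if allocation is already under way.

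Optionally, if the lists are not yet in use, amend Sections 2 and 4 to use separate permuted-block lists by the same band. This prevents the imbalance but adds little power beyond the stratified test. It costs a second set of cards and an incomplete last block in each band, so arm sizes may differ by a few infants. It should be adopted only together with the stratified analysis, because a plain log-rank test would then be conservative.

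### Infants are removed from the study after randomisation when a clinician objects or asks to be unblinded, which contradicts intention to treat and may be selective by cord-clamping arm

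*Combined protocol and SAP*

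**What the plan says.** There are three ways for an infant to leave after assignment.

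- **Neonatologist's objection (protocol section 2, Study Design).** The order is explicit: "randomization will occur in all cases", and then "if this physician has an objection to the randomization of indomethacin treatment for a specific patient that patient will be excluded from the study".
- **Obstetrician's objection (section 2, next sentence).** "Similar provisions are afforded to the delivering Obstetrician regarding delay of umbilical cord clamp randomization and treatment".
- **Request for unblinding (section 6, Research Procedures).** If the obstetrician or neonatologist has a medical concern and wishes to know the assignment, "the study participant will be removed from the study". No time limit is given.

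One exclusion criterion in section 3 also rests on clinical judgement around delivery: "if the attending obstetrician or neonatologist decides that infant requires immediate resuscitation for either maternal or newborn well-being". It applies to all arms, but its timing relative to the opening of the randomisation card is not stated.

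The text is unclear on who knows the assignment. Section 2 says "clinicians will be blinded to this choice prior to the delivery". Section 4 says that, on notice of an impending birth, "the research coordinator will open the randomization card, review the protocol with the attending/fellow/or resident obstetrician, and time the cord clamping". Section 6 expects that "the only practitioner who is unblinded in the study is the specific Neonatologist" at the delivery, without saying whether this means the cord assignment, the drug, or both.

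The SAP (Aim 1 Statistical analyses) states that analyses follow intention to treat, qualified by a phrase limiting this to cases where it is suitable. It does not say which cases those are. No analysis set is defined.

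**The concern.** Intention to treat means that every randomised infant is analysed in the assigned group. A rule that randomises first and then takes infants out of the study cannot deliver that unless the removed infants are still followed and analysed, and nothing in the documents says they are. This conflict holds whether or not the removals are selective.

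Selectivity is the further risk, and it differs by factor. Indomethacin is masked with a matched placebo, so objections made blind should fall about equally on drug and placebo. The cord assignment appears to be known to the obstetrician before birth. The obstetrician's provision concerns the delay, and section 6 describes immediate clamping as standard procedure. Objections would therefore most plausibly arise in the two DCC arms. If those infants are also at higher risk, removing them leaves a healthier DCC group and makes DCC look beneficial in Aims 1A and 1B.

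Removal on medical concern could also take infants with suspected drug toxicity out of the renal and safety comparisons. The documents give no basis for a figure on that.

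**Working it through.** **Text.** Read together, sections 2 and 6 put removal after assignment: section 2 by its stated order, and section 6 because unblinding presupposes an assignment. No sentence provides for follow-up, counting by arm, or analysis of removed infants. The intention-to-treat statement is therefore contradicted without any arithmetic.

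**Size of the possible bias (illustration).** There is no figure in the plan to reproduce here: it gives no removal rate or event rate. From the documents: 100 infants per arm (section 4), hence 200 v 200 for DCC against immediate clamping (ICC), and chi-square tests of proportions as the basis for power (SAP, Aim 3). Assumed: no true effect, 20% failure in retained infants, and removal of a fraction *f* from the DCC arms only, at failure risk *r*.

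- ICC risk, all infants kept: *f*·*r* + (1 − *f*)·0.20
- DCC risk after removal: 0.20
- Spurious benefit: *f*·(*r* − 0.20)

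Central case, *f* = 0.10 and *r* = 0.50:

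1. ICC risk = 0.10 × 0.50 + 0.90 × 0.20 = 0.23, against 0.20. Odds ratio = (0.20/0.80)/(0.23/0.77) = 0.84.
2. Pooled two-sided z test, 200 v 180: common proportion = (46 + 36)/380 = 0.216. The standard error is 0.0423 under equality and 0.0421 otherwise. Rejection rate = Φ[(0.03 − 1.96 × 0.0423)/0.0421] + Φ[(−0.03 − 1.96 × 0.0423)/0.0421] = 0.105 + 0.004 = 0.109.
3. Four-group chi-square, 3 df, arms of 100, 100, 90 and 90: noncentrality λ = Σ nᵢ(pᵢ − 0.216)²/(0.216 × 0.784) = 0.50. The probability of exceeding 7.81 is 0.081.

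| Removed from DCC arms | Their risk | ICC v DCC | Spurious benefit | False positive, four-group | False positive, pooled |
|---|---|---|---|---|---|
| any | 20% | 20% v 20% | 0 | 5.0% | 5.0% |
| 2% | 40% | 20.4% v 20% | 0.4 points | 5.1% | 5.1% |
| 2% | 60% | 20.8% v 20% | 0.8 points | 5.2% | 5.4% |
| 5% | 40% | 21% v 20% | 1 point | 5.3% | 5.7% |
| 5% | 60% | 22% v 20% | 2 points | 6.4% | 7.7% |
| 10% | 50% | 23% v 20% | 3 points | 8.1% | 10.9% |
| 20% | 60% | 28% v 20% | 8 points | 28.1% | 41.8% |

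Simulation (100,000 trials per setting) gave the same central values, and 4.8–5.2% when the same infants were retained and analysed as assigned.

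**Second parameterisation.** Hold overall risk at 20% and let removed infants have *m* times that risk. With 10% removed and *m* = 2, DCC risk becomes (0.20 − 0.10 × 0.40)/0.90 = 0.178: a spurious benefit of 2.2 points and a pooled false-positive rate of 8.5%. With *m* = 3 these are 4.4 points and 20%. Direction and scale agree.

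**Cost of retaining infants who did not receive their assignment.** Assume 70% v 87% event-free and 100 per arm. If a fraction *g* of the better arm does not receive its assignment, its rate is (1 − *g*) × 0.87 + *g* × 0.70. Power is 84% at *g* = 0, 79% at 5%, 74% at 10% and 63% at 20%.

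**The case against.** The strongest reply is that selectivity is inferred, not documented. The most explicit exclusion sentence concerns the masked drug. Selectivity by cord arm rests on the one sentence about the obstetrician plus the card-opening procedure in section 4, and section 2 says clinicians are blinded before delivery. An objection to randomisation could also mean an objection to the infant being randomised at all, which would not depend on arm. In addition, section 3 already excludes severe maternal haemorrhage, hypertensive crisis and need for immediate resuscitation in all arms. These are the obvious reasons to refuse a delay, so few arm-dependent removals may remain. The upper figures need 20% of DCC infants removed at 60% risk, which nothing in the documents suggests. The tests modelled are unadjusted, whereas the SAP plans covariate-adjusted logistic regression. The bias and power illustrations also use different baselines (20% and 30% failure), so one cannot be netted against the other.

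Much of this stands as a limit on size: selectivity is a risk, and at low removal rates it matters little. It does not answer the main point. The alternative reading of an objection fits poorly with a sentence that first says randomisation happens in every case, and it cannot apply to requests for unblinding. The section 3 criteria protect the comparison only if applied before the card is opened, which is not stated. Whether the obstetrician knows the cord arm is itself contradictory and needs settling.

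It is also fair to say that the 7- and 30-day head ultrasounds and the developmental visits are standard care, so much outcome data would exist anyway. That makes the fix cheaper, but it does not supply a rule that the data be used.

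**Conclusion.** The concern holds. The plan as written removes randomised infants with no provision to follow or analyse them, and this contradicts its intention-to-treat statement. That conclusion rests on the text alone and needs correction before analysis, because outcomes not collected on removed infants may not be recoverable.

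Bias in favour of DCC is conditional on removals depending on both cord assignment and prognosis. Under the assumptions above, 5–20% removed at 40–60% risk gives 1–8 points of spurious benefit, with false-positive rates of about 5–28% (four-group) and 6–42% (pooled). The removal rates and risks are assumptions, and the upper ends are extreme.

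**What to change.** Leave clinicians' authority over care as it is, and separate departure from assigned treatment from loss of data.

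- **Protocol sections 2 and 6:** replace exclusion or removal from the study with retention for outcome collection and analysis in the assigned group. Record non-receipt of the assignment and unblinding as deviations, reported by arm and reason.
- **SAP, Aim 1:** drop the qualifier on intention to treat for Aims 1A and 1B. Define the primary set as all randomised infants analysed as assigned, except those found ineligible on objective criteria that cannot depend on assignment, such as congenital anomaly. A per-protocol set may serve as a sensitivity analysis.
- **Section 3:** leave the resuscitation criterion unchanged. Record whether the judgement came before or after the card was opened, and keep infants judged afterwards in the primary set. This concerns the analysis set, not care.
- **Sections 2, 4 and 6:** reconcile who knows the cord assignment and when, and state to which factor the delivery neonatologist is unblinded.

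The cost is wording plus outcome collection on the retained infants: 4 to 40 of 200 DCC infants at the assumed 2–20%. The statistical price is dilution, with power falling from 84% to 74% if 10% of one arm does not receive its assignment, under the 70% v 87% assumption.
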